## 7.2 Semi-structured Qualitative Interview

A brief semi-structured feedback interview will be conducted to gain additional insights and feedback for modifications needed to the intervention to optimize it. Immediately after the escape room session, a nutrition expert will facilitate a 15-20 minute group interview with the participants to give them an opportunity to reflect on their experience with the game. The objective of the semi-structured group interview is to understand how participants’ attitudes and feelings about misinformation may have been impacted by the escape room experience. The interview will also explore how vulnerable participants feel to health information and their comfort level with questioning the source and nature of information. The nutrition expert will use a short

interview guide (9 questions) to facilitate the group interview. The role of the facilitator will be to elicit people's opinions and allow others to carry the conversation, making sure the discussion stays on topic and stepping in to provide additional information as a nutritional expert.

## 8.0 PARTICIPANT WITHDRAWAL

Participants can discontinue participating at any time and for any reason, including during a study interview.

## 9.0 CONCOMITANT MEDICATIONS

N/A

## 10.0 ADVERSE EVENTS

### 10.1 Adverse Event

This is a low-risk, behavioral intervention study. Any adverse events will be recorded in the Adverse Event Summary Form and reported as follows.

### 10.2 Adverse Event Grading Scale

**0 = No Adverse Event** or within normal limits.

**1 = Mild Severity:** Transient laboratory test alterations; discomforts noted but no disruption of daily activities; no therapy, or only symptomatic therapy required.

**2 = Moderate Severity:** Laboratory test alterations indicating injury without long-term risk; discomfort sufficient to modify normal daily activity; specific therapy required (i.e., more than symptomatic).

**3 = Serious Severity:** Laboratory test indicating a serious health threat or permanent injury; incapacity, inability to work, inability to perform normal daily activity; hospitalization required or prolonged; emergency treatment required; life-threatening events; death.

**Plan for unanticipated AE reporting:** All unanticipated AEs related to the study procedures that are severe or serious will be reported by [name] to the IRB within 10 days of notification of the investigator.

**Plan for anticipated AE reporting:** All anticipated AEs related to the study procedures will be documented in the study's Reportable Events Log.

**Plan for ongoing review of results:** The PI will be notified within 24 hours by the research manager of any early terminations due to an adverse event.

**Plan for safety review:** The PI will perform a cumulative review of all adverse events and premature terminations review every 3 months after study initiation or after completion of 50% of participant visits, whichever occurs first.

**Plan for annual reporting:** A summary of the investigation including all adverse events and how they were handled, enrollment, drop-outs and reason for discontinuation and any protocol modifications will be provided to the IRB on an annual basis.

Annual Reports will contain:

- a. The number of adverse events and an explanation of how each event was handled.
- b. The number of complaints and how each complaint was handled.
- c. The number of participant withdrawals and an explanation of why the participant withdrew or was withdrawn.
- d. The number of protocol deviations and how each was handled.

The occurrence of any serious and unexpected event may prompt changes in study protocol. Any such change will be approved by the IRB before implementation.

### 10.3 Serious Adverse Event (SAE)

An adverse event should be classified as an SAE if it meets one of the following criteria:

Fatal	Adverse event results in death.
Life threatening:	The adverse events placed the participant at immediate risk of death. This classification did not apply to an adverse event that hypothetically might cause death if it were more severe.
Hospitalization:	It required or prolonged inpatient hospitalization. Hospitalizations for elective medical or surgical procedures or treatments planned before enrollment in the treatment plan or routine check-ups are not SAEs by this criterion. Admission to a palliative unit or hospice care facility is not considered to be a hospitalization.
Disabling/incapacitating	Resulted in a substantial and permanent disruption of the participant's ability to carry out normal life functions.
Congenital anomaly or birth defect:	An adverse outcome in a child or fetus of a participant exposed to the molecule or treatment plan regimen before conception or during pregnancy.
Medically significant:	The adverse event did not meet any of the above criteria but could have jeopardized the participant and might have required medical or surgical intervention to prevent one of the outcomes listed above.

### 11.0 DATA AND SAFETY MONITORING PLAN

This is a low-risk, behavioral intervention study. To ensure data safety and accuracy, the measures described below will be taken.

Table 2 below describes each data monitoring activity, responsible staff person, and frequency of review. Tracking forms will be developed to document the occurrence of all reviews. The PI will review all reports as they are generated. Study data will be stored on a secure network and the file will be password protected. A file linking participants' names and study ID numbers will be stored separately from the data file. This file will also be stored on a secure network and password protected. Only study staff will have access to these files and the passwords will be changed in the event of study staff turnover.

**Table 2. Data monitoring**

Activity	Report	Timing of review by PI
Study Recruitment	Weekly report generated by CRC	Weekly PI review
Enrollment	Weekly report generated by CRC	Weekly PI review
Study Retention	Weekly report generated by CRC	Weekly PI review
Informed Consent	Quality control of each new consent	PI reviews all consents upon receipt
Interviews/Self-Report Measures	PI and other study staff will review all interview and self-report materials and complete fidelity checklist	PI will review data weekly for completeness and accurate entry into a spreadsheet for analysis

A data safety and monitoring committee is not needed as this is not a Phase 3 clinical trial. [name] (PI) will oversee the data safety and monitoring for this project. She will meet with the study staff to discuss protocols and procedures to ensure participant safety and the validity and integrity of the study data. All staff

members will attend trainings on these procedures and will be given information on the importance of reporting any adverse event immediately. [name] and the IRB will be alerted about any adverse events immediately. [name] will discuss any adverse effects and examine available data to assess whether safety is compromised. Action to resolve the adverse event will be discussed with IRB prior to implementation. The team will enact any actions recommended by the IRB.

## 12.0 DATA MANAGEMENT/CONFIDENTIALITY

### REDCap

We will use REDCap to track, collect and maintain study data. REDCap is a web-based electronic data capture system. Using the HIPAA-compliant REDCap platform, we will design, build, and maintain the data forms that will be used for data capture, including screening, consenting, participant questionnaires, and staff forms for participant tracking.

## 13.0 STATISTICAL CONSIDERATIONS

### 13.1 Study Design

The current study is an open, single-arm trial.

### 13.2 Analyses

Feasibility, acceptability, and usability will be examined by conducting frequency and descriptive statistics for Likert-scale questions and SUS scale. We will conduct preliminary pre/post analyses using repeated measures analysis of variance (ANOVAs) on the misinformation belief scales to assess changes in these beliefs. Finally, we will conduct qualitative analyses on the open-ended questions using a responsive interviewing model for data coding and analysis in which data units or “blocks of information that are examined together” (p. 202) are combined based on the theme they represent. Trained raters will independently review the transcripts and identify passages that include information on participants’ suggestions for modifications to the escape room game. The themes identified in this analysis will inform additional revisions to the intervention as determined by the study investigators.

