## 2.3 Risks/Benefits

### Risks

- Discomfort. There may be some emotional discomfort in discussing misinformation and disinformation rhetoric in relation to health and nutrition related topics. We do not anticipate that this discomfort will be exacerbated by a group setting. Indeed, misinformation researchers use group reflection meetings to mitigate the emotional impact of being exposed to misleading and problematic information. The UW's Center for an Informed Public builds group reflection meetings into research timelines for their student researchers as group reflection on misleading information has allowed researchers to maintain clarity in confusing information environments and provided them with a supportive space to share any concerns around the information they encounter. We anticipate that this same framework will apply to the cancer patient population. Further, the Misinformation Escape Room has been designed using expert insight from in-depth interviews with oncologists and cancer nutrition experts and will be, prior to player testing, evaluated by the same experts to ensure it is appropriate for this specific patient population. Finally, we have proper oversight and monitoring of any adverse events created by participating in group settings in order to ensure an accurate oversight of and response to any potential distress is part of the research plan. Participants can decline to complete the intervention, survey or interview or skip questions at their own discretion.
- Loss of privacy. A risk of taking part in this study is the possibility of a loss of confidentiality. Loss of confidentiality includes having your personal information shared with someone who is not on the study team and was not supposed to see or know about your information. We will try to protect your information, but we cannot guarantee privacy. The plans for keeping your information private are described in the 'confidentiality' section of this consent form.

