## 6.2 Estimated Accrual

Our goal is to consent 40 study participants total (8 groups of n=5). Based on clinic volume and patient flow, we estimate that we can approach and consent n=40 patients within 6 months. On average, in each year of 2020 and 2021, approximately 1,659 new breast cancer patients were diagnosed and treated at Fred Hutch (formerly SCCA), with 1,492 being stage 0-III breast cancer patients. Thus, our proposed recruitment goal is achievable. If a patient drops out prior to the intervention, they will be replaced to reach a final n of =40.

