## 7.0 PARTICIPANT EVALUATION

### 7.1 Study Questionnaires and Assessments

- **Background information**
  - *Demographic and disease characteristics* will include age, gender, race/ethnicity, education level, marital and parental status, income, cancer type, date of diagnosis, and cancer stage.
  - *Behaviors done based on information consumed online* will be assessed with a 6-item checklist asking which behaviors participants have done because of something they saw on the Internet (e.g., "Taken an over-the-counter medicine or supplements, for example, vitamins, minerals, or nutritional supplements").
- **Aim 1:**
  - *Feasibility* will be assessed by rates of accrual and completion of game sessions.
  - *Acceptability* will be assessed using two Likert-type scales to assess satisfaction (1 = not at all satisfied, 10 = very satisfied) and likelihood to recommend the game to someone else (1 = not at all likely, 5 = very likely).
  - *Usability* will be assessed using the System Usability Scale (SUS). The SUS is a reliable, 10-item measure 10-item scale, scored on a 5-point Likert scale (1=strongly disagree; 5=strongly agree), with previously reported excellent internal reliability (Cronbach's  $\alpha = 0.91$ ).
- **Aim 2:**

- *Types of online information* (e.g., *sources of nutrition information utilized*) will be assessed using a 6-item checklist that asks which resources participants or their family members have used to find nutrition information in the past 3 months (i.e., a self-care/health and wellness book, a telephone advice service, a booklet/flyer shared by a health professional, Internet forums, Internet search, social media).
- *Concern about misinformation and confidence in identifying misinformation* will be measured using our 4-item scale in which patients indicate degree to which they agree with statements (e.g., “I feel more confident in my ability to identify misinformation”; 1= strongly disagree, 5 = strongly agree).
- *Cancer nutrition information beliefs* will be measured using a 15-item checklist of common cancer nutrition misinformation and credible nutrition advice. Participants rate the items on a 5-point Likert-scale (1= definitely false, 5 = definitely true).
- **Exploratory outcomes:**

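### If any post-game surveys are missing, the Aim 2 ANOVA drops those patients; a mixed model on all observed belief scores is a free improvement

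*Combined protocol and SAP*

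**What the plan says.** All references are to the combined protocol and SAP.

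- **Method.** Section 13.2 plans "preliminary pre/post analyses using repeated measures analysis of variance (ANOVAs) on the misinformation belief scales". It does not define an analysis set, and it does not say what happens to a missing survey or a partly answered scale. It names no sensitivity analysis.
- **Missing data are allowed.** Section 2.3 (Risks): "Participants can decline to complete the intervention, survey or interview or skip questions at their own discretion". Section 8.0: "Participants can discontinue participating at any time and for any reason, including during a study interview".
- **Replacement.** Section 6.2: "If a patient drops out prior to the intervention, they will be replaced to reach a final n of =40". Nothing is stated for a patient who plays the game but returns no post survey.
- **Outcome.** Section 7.1 describes the belief measure as a "15-item checklist of common cancer nutrition misinformation and credible nutrition advice", each item rated 1 to 5. Section 6.3, including Table 1, places it at baseline and after the intervention.
- **Use.** Section 3.1 calls Aim 2 exploratory. Sections 2.1 and 3.1 say the pilot supplies preliminary data for an application to run a full randomized trial.

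**The concern.** A repeated measures ANOVA with two time points is a paired t-test (F = t²). A patient with a baseline score and no post score contributes nothing to it. The target of 40 in section 6.2 is protected only up to the start of the intervention. The post survey is a separate task after the game and debrief, so attending the session does not guarantee a post score.

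Two things are at stake. The first is precision, because fewer pairs give a wider interval. The second is bias. Patients with stronger misinformation beliefs at baseline have more room to fall, through regression to the mean. If they are also less likely to return the post survey, the complete pairs understate the reduction; if weaker believers are the ones who fail to return, the complete pairs overstate it. The resulting change is the figure carried into planning the next trial.

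**Working it through.** **Inputs from the documents.** N = 40, which reproduces as 8 groups × 5 (section 6.2). Two measurement times and 15 items per time, so 30 item responses per patient (sections 6.3 and 7.1). No power, effect size, SD, correlation or loss rate is given for Aim 2, so there is no efficacy calculation to reproduce.

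**Assumptions.** SD 1 at both times; pre/post correlation ρ = 0.5 unless stated; post-survey loss 0 to 30%. With ρ = 0.5 the SD of change is √(2(1 − 0.5)) = 1, so one SD of change equals one baseline SD.

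**1. Precision of complete pairs.** 95% CI half-width = t(0.975, n − 1)/√n, in SDs of change.

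| Assumed loss | Pairs | Half-width |
|---|---|---|
| 0% | 40 | 0.320 |
| 10% | 36 | 0.338 |
| 20% | 32 | 0.361 |
| 30% | 28 | 0.388 |

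The interval is 6% to 21% wider at 10% to 30% loss.

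**2. Bias of complete pairs when loss depends on baseline.** Let m be the share missing and D the amount by which non-returners exceed returners at baseline. The returners' baseline mean is then mD below the full mean, and expected change shifts by (1 − ρ) per unit of baseline. So bias = (1 − ρ) × m × D.

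- D = 0.5: 0.5 × 0.2 × 0.5 = 0.05 SD.
- D = 1.0: 0.5 × 0.2 × 1.0 = 0.10 SD.
- Complete-pair SE at n = 32: √(1/32) = 0.177 SD.

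The bias is therefore about 0.3 to 0.6 of a standard error.

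**3. What a mixed model recovers.** Using all 40 baselines and 32 post scores, the large-sample SE is √((1 − ρ²)/32 + (1 − ρ)²/40) = √(0.75/32 + 0.25/40) = 0.172, against 0.177. The precision gain is about 3%. The main benefit is removal of the step 2 bias.

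**4. Simulation.** True change −0.30 SD, 20% missing.

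| Odds of missing | ρ | Complete pairs | Likelihood-based (mixed model) |
|---|---|---|---|
| Double per SD of baseline belief | 0.5 | −0.24 | −0.30 |
| Double per SD of baseline belief | 0.7 | −0.26 | −0.30 |
| Double per SD of change (rise in belief) | 0.5 | −0.43 | −0.40 |
| Double per SD of change (rise in belief) | 0.7 | −0.40 | −0.39 |

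The first two rows agree in size with step 2. The last two show that neither method is safe when loss depends on the change itself.

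**5. Skipped items (secondary).** If, and only if, every item had to be answered, the share with both scores complete would be (1 − q)^30 for an independent per-item skip rate q. At q = 1% this is 0.740 (about 30 of 40); at 2% it is 0.545 (about 22 of 40). Accepting at least 12 of 15 answered at both times keeps 0.9996 at q = 2%.

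**The case against.** **Loss may be small.** Participation is 90 minutes with one session (synopsis), the post-survey column in Table 1 is headed + 1 week, the $75 payment covers both surveys (section 2.3), and the PI reviews data weekly for completeness (Table 2). The wording on skipping and withdrawal is ordinary voluntary-participation text. This stands: if all 40 return both surveys, nothing is lost. But the weekly review is data monitoring and not an analysis rule.

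**The mixed model adds little.** A 3% gain in SE is slight, the bias is below one standard error, and the size of D has no basis in the documents. When loss depends on the change itself, the model is nearly as biased as the pairs. This also stands, and it limits the claim. It does not favor the ANOVA, which has no advantage here to set against the model.

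**Consequences are low.** The Aim 1 hypotheses do not use this analysis, and no alpha, power or decision rule rests on Aim 2. Agreed.

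**A stronger reading that the documents do not support.** A reader might infer that one skipped item removes a patient, so that the analysis shrinks to 22 of 40. Nothing in the protocol says a skipped item voids a scale. The 1% and 2% rates are assumed, as is independence; skips concentrated in a few patients would leave more complete records. Nor is it stated that all 15 items enter the analyzed score: the list mixes misinformation with credible advice, while section 13.2 refers to misinformation beliefs. With 10 items (an assumption), 0.99^20 and 0.98^20 leave about 33 and 27 of 40. The missing scoring rule is a detail that analysts would probably fill sensibly.

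**Conclusion.** The point holds as a free improvement of low severity. The restriction to patients with both scores is not written in the plan; it follows from the named method, and no alternative is specified. Its effect depends on post surveys actually being missing, which the documents do not quantify. Under the illustrative 20% loss, the cost is a CI half-width of 0.361 rather than 0.320 SD, plus a bias of about 0.05 to 0.10 SD if non-returners start 0.5 to 1.0 SD higher. That is worth avoiding when the remedy is only wording, but it does not make the ANOVA invalid or threaten the main aim. The range of 22 to 30 of 40 analyzed is an assumed worst case under a strict all-items rule, and should not be cited as the expected loss.

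**What to change.** In section 13.2:

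1. Replace the ANOVA with a linear mixed model for repeated measures, with time as a fixed effect and an unstructured covariance for the two times, fitted by REML to all observed baseline and post scores.
2. Report the number of patients contributing at each time, and compare baseline scores of those with and without a post score.
3. Give the complete-pair result as a sensitivity analysis. State that the mixed model corrects only missingness explained by observed data, so neither result covers loss that depends on the change itself.
4. As a secondary point, set item direction or subscales first. Then score each scale as the mean of answered items when at least 80% are answered (12 of 15 if all belief items form one score).

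The cost is SAP wording only, with the same patients, surveys and data. With complete data the model reproduces the ANOVA result.

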### 13.4 Ethnic and Gender Distribution Chart

We will recruit cancer patients who are treated at Fred Hutchinson Cancer Center, which reflect the demographics for the Seattle area and the previously SCCA population. Based on the demographics of the entire SCCA oncology patient population since 2001 (for which data is currently available), 78.6% of cancer patients are female. Patient race/ethnicity distribution in this population are 53.2% White, 10% Asian, 6.8% Black or African Americans, 1.3% Alaskan Indian or Alaskan Native, 1.2% Hispanic, 1.1% other, 0.8% Native Hawaiian or Other Pacific Islander, 0.3% multiracial, and 25.3% unknown. The projected target patient accrual for this study is based on these estimates. Due to this recruiting a breast cancer patient population, we anticipate recruiting female only patients.

Projected Target Accrual  
ETHNIC AND GENDER DISTRIBUTION CHART

TARGETED / PLANNED ENROLLMENT: Number of Subjects			
Ethnic Category	Sex / Gender		
	Females	Males	Total
Hispanic or Latino	1	0	1
Not Hispanic or Latino	39	0	39
Ethnic Category Total of All Subjects*	40	0	40
Racial Categories			
American Indian / Alaska Native	1	0	1
Asian	4	0	4

Native Hawaiian or Other Pacific Islander	1	0	1
Black or African American	2	0	2
White	32	0	32
More Than One Race	0	0	0
Unknown	0	0	0
Racial Categories: Total of All Subjects*	40	0	40

**14.0 INVESTIGATOR OBLIGATIONS**

The PI is responsible for the conduct of the study at the site and is responsible for personally overseeing the treatment of all study participants. The PI must assure that all study site personnel, including Co-Investigators and other study staff members, adhere to the study protocol and to all applicable regulations and guidelines regarding proper research protocols both during and after study completion. All participants are informed of the nature of the study, its possible risks, and their right to withdraw at any time, and each participant signs a form indicating their consent to participate prior to engaging in any study-related procedures.

